5.3.7 Criteria for hypoglycaemic events

Every episode of plasma glucose ≤ 70 mg/dl (≤ 3.9 mmol/l) should be documented in the eCRF with the respective time and date of occurrence. Such hypoglycaemic events should be documented in the eCRF according to the following criteria:

- Asymptomatic hypoglycaemia: event not accompanied by typical symptoms of hypoglycaemia but with a measured plasma glucose concentration ≤ 70 mg/dl (3.9 mmol/l)
- Documented symptomatic hypoglycaemia with glucose concentration ≥ 54 mg/dl and ≤ 70 mg/dl (≥ 3.0 mmol/l and ≤ 3.9 mmol/l): event accompanied by typical symptoms of hypoglycaemia
- Documented symptomatic hypoglycaemia with glucose concentration < 54 mg/dl (< 3.0 mmol/l): event accompanied by typical symptoms of hypoglycaemia
- Severe hypoglycaemic episode: Event requiring the assistance of another person to actively administer carbohydrate, glucagon or other resuscitative actions.

Note for severe hypoglycemia: If another person hands the carbohydrate or glucagon to the patient without having to actively administer the substance because the patient is able to take the substance on his or her own, the hypoglycaemic episode does not qualify as severe.

Any hypoglycaemia with glucose values < 54 mg/dl (< 3.0 mmol/l) and all symptomatic or severe hypoglycaemia events should be documented as an adverse event of hypoglycemia.

Further details on documentation of hypoglycemia are provided on the respective eCRF pages.

5.7 APPROPRIATENESS OF MEASUREMENTS

All measurements performed during this trial are standard measurements and will be performed in order to monitor safety aspects in an appropriate way.

The scheduled measurements are appropriate to see drug induced changes in vital signs, standard laboratory values, biomarkers specific to efficacy of treatment of T2DM, and ECG. The primary and secondary endpoints are standard and accepted for evaluation of safety and tolerability of an oral antidiabetic drug, and they are widely used in respective pivotal phase III studies.

Therefore, the appropriateness of all measurements applied in this trial is given.

6. INVESTIGATIONAL PLAN

6.1 VISIT SCHEDULE

All trial visits should be routinely scheduled in the morning, at approximately the same time of day (07:00 AM to 11:00 AM). If a patient mistakenly takes trial medication on the morning of a visit before attending the trial site (excluding visits starting before randomisation) or comes in non-fasted where a fasting condition is required (all visits except screening), the visit should be rescheduled for another day as soon as possible reminding the patient about the expected conditions. The rescheduled visit must take place in a short enough time-frame so that the patient has sufficient trial medication available.

All patients are to adhere to the visit schedule as specified in the [Flow Chart](#). If any visit has to be rescheduled, subsequent visits should follow the original visit date schedule. The trial medication packs contain sufficient medication to allow for these time windows.

6.2 DETAILS OF TRIAL PROCEDURES AT SELECTED VISITS

6.2.1 Screening and run-in period

Screening Period

The screening visit is the only visit in this study that does not need to be done fasting.

No trial procedures should be done unless the patient has consented to taking part in the trial.

Once patients have consented, the patient is considered to be enrolled in the trial and have started screening. The patient should be recorded on the enrolment log and be registered in the IRT as a screened patient.

Patients who fail screening following Visit 1 procedures should be registered as a screen failure in the IRT (refer to IRT user manual).

Run-in Period

From this visit on, patients should be fasting (no food or drinks, water only for at least 10 hours) prior to each visit.

Patients who fail the run-in period following Visit 2 procedures should be registered as a screen failure in the IRT (refer to IRT user manual).

The patients can take their background medication as they are used to, where it is suggested that basal insulin is always given in the evening. Morning dose of metformin/any permitted pre-mixed insulin and study medication should be taken after the visits blood sample collection, and the patients should have the same habits of dosing throughout the trial.

Monitor adverse events, document in the patients file (source data) and eCRF. For patients that fail on screening before or at this visit, only serious AE's that took place between screening and this Visit 2 must be recorded in the eCRF and the SAE form.

Instruct patients on the correct use of HBGM for glucose testing during the 2 week Run-In Period

- Patients should use the HBGM equipment/supplies to test glucose levels in a fasting state. During the Run-in period patients should test once a day before breakfast (i.e. after an overnight fast). Additionally, patients should test their glucose levels if they experience signs/symptoms of hypo- or hyperglycaemia. Test results should be documented on the HBGM testing log. More frequent HBGM testing is permitted at the Investigator's and/or patient's discretion.
- If the HBGM test reveals an overnight fasted blood glucose of >240 mg/dl (>13.3mol/l), the patient should contact the study site for a visit at the next day. The investigator will then draw a new blood sample (overnight fasted samples for FPG determination) to confirm the hyperglycaemia, document the AE if appropriate and decide about the possible exclusion from randomisation (screening failure).

Baseline Conditions

Chronic diseases, current observable conditions, any new clinically relevant findings discovered from the physical examination, ECG, safety labs, and any condition requiring therapy (excluding T2DM) will be reported on the Baseline Condition eCRF page.

Medical History

Medical history will be collected and reported in the Medical History eCRF page.

6.2.2 Treatment period

The treatment period is from Visit 3 to Visit 8. Patients will be dispensed medication at each of these visits (except for Visit 8). Medication number of each occasion will be allocated by IRT (refer to IRT user manual).

Patients should not take study medication at home on the morning of trial visits during the treatment period.

Randomisation visit (Visit 3)

Visits should be performed fasting and as indicated in the [Flow Chart](#) and the respective protocol sections.

Randomisation/treatment allocation and dispensing of study medication should be the last activity at this visit.

Visits 4-8

Visits should be performed as mentioned in the Flow Chart and the respective protocol sections.

If a patient prematurely discontinues from the 24-week treatment period, the patient must return to the trial site for both Visit 8 (within 7 days of stopping study treatment) and Visit 9 (7 days after Visit 8), which will be performed.

The investigator may initiate any additional antidiabetic therapy for the patient, based on his or her discretion, no sooner than one day after discontinuing study medication or after Visit 8.

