Patients who drop out during the screening phase prior to randomisation (Visit 3) will be considered a screening failure. They have to be recorded as screening failure in eCRFs and no further follow-up is required.

Patients who discontinue or withdraw from the study after randomisation (Visit 3) will be considered as “early discontinuations” and the reason for premature discontinuation must be recorded in the eCRFs. The data will be included in the trial database and will be reported. If determined by investigator as necessary for patient safety, new antidiabetic medication regimen can be started immediately after discontinuation and must be recorded in eCRFs.

Patients who withdraw or discontinue from the trial after randomisation will not be replaced.

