7.3.1 Primary endpoint analyses

The primary analysis will be performed on the FAS and patients will be assigned to the treatment they were randomised to. A REML-based MMRM approach is applied to compare the change in HbA_{1c} from baseline after 24 weeks of treatment ([Section 7.2](#)).

The statistical model will be

HbA_{1c} change from baseline = overall mean + baseline HbA_{1c} + treatment + type of insulin
+ week+ week by treatment interaction
+ baseline HbA_{1c} by week interaction
+ random error

This model includes effects accounting for the following sources of variation: ‘baseline HbA_{1c}’, ‘treatment’, ‘type of insulin (basal insulin or any permitted pre-mixed insulin)’, ‘week’, ‘week by treatment interaction’ and ‘baseline HbA_{1c} by week interaction’. ‘Treatment’, ‘type of insulin’, ‘week’ and ‘week by treatment interaction’ are fixed, categorical effects, and ‘baseline HbA_{1c}’ and ‘baseline HbA_{1c} by week interaction’ are continuous, linear covariates. For each patient, the error terms from the on-treatment visits represent the within-patient variability, and are assumed to follow a multivariate normal distribution with an unstructured covariance matrix.

If the model fails to converge, further covariance structures will be tested, details will be provided in the TSAP. The first model to converge will be used as the primary analysis. The Kenward-Roger approximation will be used to estimate the denominator degrees of freedom. Significance tests will be based on least squares means using a two-sided $\alpha=0.05$ (two sided 95% confidence intervals).

Only the available data which were observed whilst patients were on treatment will be included in the analysis. Missing data are handled implicitly by the above statistical model,

rather than by using any imputation. This approach, referred to as observed case (OC), will additionally set to missing all values measured after rescue medication use.

Superiority will be tested using the p-value of the treatment effect and a two-sided 95% confidence interval for the treatment difference.

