16.1.9 Documentation of statistical methods

Proprietary confidential information © 2019 Boehringer Ingelheim International GmbH or one or more of its affiliated companies

Boehringer Ingelheim

TSAP for BI Trial No: 1218.102

Proprietary confidential information © 2019 Boehringer Ingelheim International GmbH or one or more of its affiliated companies

Table 6.7: 1 Endpoint specific follow-up period for the assignment to active treatment

| Endpoint | Last day of assignment to treatment phase (days after study drug stop date) |
|---|--|
| Efficacy | |
| HbA _{1c} | 7 |
| FPG | 1 |
| PPG, | 0 |
| Body weight | 7 |
| Waist circumference | 7 |
| Rescue medication (new antidiabetic treatment, increases of background antidiabetic treatment) | |
| If patient did not prematurely discontinue from trial medication | -1 |
| If patient prematurely discontinued from trial medication (any reason) | 0 |
| Safety | |
| Adverse events | 7 |
| Safety laboratory measurements | 7 |
| Vital signs | 7 |

Measurements taken after the end of the follow-up period after the last intake of study drug will be considered post-treatment values.

On-treatment efficacy measurements will be assigned to visits based on time windows around the planned visit dates. These time windows are defined based on the planned number of days after the date of first administration of study drug (usually this is at Visit 3). Reasons to base the time windows on the actual treatment start date rather than the randomisation date are:

- If first intake of study drug shows a large delay by e.g. more than one week after the date of randomisation, a measurement taken four weeks after randomisation rather reflects the drug effect after three weeks than after four weeks and thus may underestimate the treatment effect at this visit.
- With large delays of the introduction of study drug after the randomization, the time window for the first on-treatment visit could include times the patients was not yet on study drug.

The time window for the first visit after randomization starts on the day after the first intake of study drug. This maximises the number of measurements used in by visit analyses and provides consistency with the planned last observation carried forward (LOCF) approach, but may lead to an underestimation of the treatment effect at the first visit form parameters that react slowly on treatment.

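### Two unlinked protocol rules on when new antidiabetic therapy may start after an early stop, and SAP windows that keep some HbA1c values drawn under that therapy

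*Protocol*

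**What the plan says.** **Start of new therapy.** Protocol 3.3.4.1, on patients who stop after randomisation, says that where the investigator finds it necessary for safety a "new antidiabetic medication regimen can be started immediately after discontinuation and must be recorded in eCRFs". Protocol 6.2.2 says that additional antidiabetic therapy may be given at the investigator's discretion "no sooner than one day after discontinuing study medication or after Visit 8". The same section requires early stoppers to attend Visit 8 within 7 days of stopping. Neither section refers to the other.

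**Handling of values.** Protocol 4.2.1 counts the introduction of any new antidiabetic therapy for at least one day as rescue. Under Protocol 7.3.1 the observed-case (OC) approach "will additionally set to missing all values measured after rescue medication use". Protocol 7.5 and SAP 6.6 repeat that rule.

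**Windows.** SAP Table 6.7:1 assigns HbA1c to treatment up to 7 days after the drug stop date and FPG up to 1 day. Its rescue row expressly includes new antidiabetic treatment, and for early stoppers it reads "If patient prematurely discontinued from trial medication (any reason) | 0", that is, zero days after the stop date.

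**The concern.** There are two separate problems.

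The first is operational. A safety-driven start on the day of discontinuation is allowed by 3.3.4.1 and, on its face, too early under 6.2.2. The wording of 6.2.2 is also unclear in itself. Its two alternatives, one day after stopping or after Visit 8, can lie up to 7 days apart, and the text does not say whether either suffices or the later one governs.

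The second is analytic. The rescue window closes on the stop date while the HbA1c window stays open for another week. A new glucose-lowering drug begun inside that gap does not trigger deletion, so an HbA1c drawn under it enters the mixed model as an on-treatment value of the randomised arm. Starting on day 1 or later is what 6.2.2 describes, so the gap coincides with the timing that section lays down. At stake is a retention rule for primary-endpoint data that turns on one calendar day.

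**Working it through.** **1. The plan's own figures.** Protocol 7.7 gives a difference of 0.55, SD 1.1, 100 per group and two-sided alpha 0.05. The standardised effect is 0.55 / (1.1 × √(2/100)) = 3.54. Power is 94.2% by the normal approximation and 94.0% by the noncentral t, against a stated 94%. For dropout, 100 / (1 − 0.022) = 102.2, rounded up to 103 per arm, or 206 in total. Both figures reproduce and are not in dispute.

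**2. The windows applied.** Let day 0 be the drug stop date, and assume no earlier rescue.

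| New therapy starts | Counts as rescue (Table 6.7:1)? | Visit 8 HbA1c drawn later, up to day 7 |
|---|---|---|
| Day 0 | Yes | Set to missing |
| Day 1 or later, before Visit 8 | No | Kept, with up to 6 days of new therapy |
| After Visit 8 | No | Kept, not exposed to new therapy |

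A sample drawn on day 0 before the new drug is kept in every case.

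Example: the last dose is on study day 150 and the Visit 8 HbA1c on day 157. Therapy begun on day 150 makes the value missing. Therapy begun on day 151 leaves it in the analysis after about 6 days of the new drug.

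**3. How many patients.** 0.022 × 206 = 4.5 dropouts in both arms together. At an assumed 5% the figure is 10.3, and at 10% it is 20.6. These are ceilings. An exposed patient must have had no earlier rescue, must start new therapy in the 7 days after stopping, and must have HbA1c drawn after that start but by day 7. The value must also be the one selected for its visit window, and SAP 6.7 prefers a sample from the last day of treatment over a later one.

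**4. How far a mean could move.** Suppose every dropout in one arm (103 × rate) is affected, with about 100 patients contributing. The shift in that arm's visit mean is then 103 × rate × d / 100.

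- *Effect of the new drug on a kept value.* Assume d = 0.05 to 0.15 points after 6 days of an agent worth about 1 point in full. At 2.2% dropout: 2.27 × 0.05 / 100 = 0.001, to 2.27 × 0.15 / 100 = 0.003.
- *Effect of keeping rather than deleting the value.* Assume it differs from its model prediction by d = 0.5 to 1.5 points. At 2.2% the shift is 0.01 to 0.03, and at 10% it is 0.05 to 0.15.

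The design difference is 0.55.

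**5. Where the value lands.** Under Table 6.7:2 a Visit 8 before day 149 goes into an earlier visit window and reaches Week 24 only through the repeated-measures model. It matters more if it is the patient's only on-treatment HbA1c, because entry to the full analysis set depends on having one. Responder endpoints are largely unaffected, since SAP 7.5.2 counts patients who do not complete 24 weeks as non-responders.

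**The case against.** The other side has a good deal to say, and much of it stands.

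- *A reader might infer that a site cannot obey both protocol sections.* That goes too far. Section 3.3.4.1 is a permission conditional on safety, so a site that waits complies with both. It also reads naturally as an exception to 6.2.2. What remains is that the protocol never says so, and a site that uses the permission has no protection against a deviation finding.
- *A reader might infer that withdrawals for lack of efficacy, expected more often on placebo (SAP 6.6), would contaminate the arms unevenly.* The documents do not support this. Protocol 3.3.4.1 applies the lack-of-efficacy label after rescue has been introduced and has failed. Where that rescue met the definition in 4.2.1, later values are already missing whatever day the next drug starts. The exposed patients are mainly those who stop for other reasons without earlier rescue, and nothing in the documents points to an imbalance among them.
- *A reader might extend the point to FPG.* Its window closes on day 1, therapy after a one-day wait starts on day 1 at the earliest, and the sample is taken fasting before breakfast. The new drug would have to be taken before that morning's sample.
- *The zero-day cut-off may be deliberate.* It may treat anything begun after the stop date as post-treatment therapy rather than rescue. SAP 6.6 refers to SAP 5.3 for the definition of rescue, and that section is not in the copy available for review, so a further rule cannot be excluded. Any such rule would still have to be squared with the zero in Table 6.7:1.
- *Keeping a slow-moving marker for 7 days is defensible.* It is, and it matches the pharmacodynamic effect of about 7 days given in Protocol 3.2. That reasoning weakens once another agent has been started.

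**Conclusion.** The point holds as a matter of consistency. Protocol 3.3.4.1 and 6.2.2 give different, unlinked start times for new antidiabetic therapy after an early stop, and 6.2.2 is itself ambiguous by up to 7 days. SAP Table 6.7:1 keeps an HbA1c drawn after therapy begun on days 1 to 7 but removes the same value if therapy began on the stop date, which is at odds with the stated handling of values after rescue.

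The numerical effect is very small: a subset of about 4 to 5 patients at the stated dropout, and at most about 0.03 points on one arm's visit mean under the widest assumption used at that rate. It does not call the primary analysis into question.

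The conclusion rests on three readings. Starting immediately must mean the calendar day of the last dose; if the last dose was the day before, the start is already day 1 and the value is kept under both rules. Visit 8 HbA1c must be drawn on days 1 to 7. And SAP 5.3 must contain no overriding rule. The per-value shifts are assumptions and are not taken from the documents.

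**What to change.** 1. **Protocol.** Reconcile 3.3.4.1 and 6.2.2 into one statement of when new antidiabetic therapy may start after early discontinuation. It should say whether the safety provision is an exception and how the two alternatives in 6.2.2 relate. Which timing applies is for the sponsor to decide; this review takes no view.
2. **SAP 6.6, OC rule.** Add that any HbA1c taken after the start of new antidiabetic therapy within the 7 days after the drug stop date is set to missing. Check the addition against SAP 5.3.
3. **SAP Table 6.7:1.** Leave the rescue row as it is for counting rescue use. Widening it would also count therapy begun after discontinuation as on-treatment rescue.

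The cost is one protocol statement and one SAP sentence, the loss of a few late Visit 8 values, and slightly more reliance on missing at random. Precision is not a serious concern. If all dropouts' values were lost, t-test power would be 94.0% at 2.2% dropout (100 per arm), 93.4% at 5% (97 per arm) and 92.1% at 10% (92 per arm).

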6.2.3 Follow Up Period and Trial Completion

For all patients completing the study according to protocol a follow-up contact (Visit 9) with the patient (preferably by phone) should be done by the investigator at the end of the follow-up period of 7 days.

In case of premature discontinuation from the 24 week treatment period however, an End of Trial Visit (V9) should be performed and the patient should return to Visit 9 (7 days after Visit 8/end of treatment). The following examinations should be performed at Visit 9:

- Vital signs
- Collection of blood and urine samples for safety laboratory evaluation
- Documentation of any adverse events
- Documentation of concomitant therapies

7. STATISTICAL METHODS AND DETERMINATION OF SAMPLE SIZE

7.1 STATISTICAL DESIGN - MODEL

The objective of this randomised, double-blind, placebo-controlled study is to investigate the efficacy and safety of linagliptin compared to placebo given for 24 weeks as add-on therapy to insulin alone or in combination with metformin in Chinese patients with T2DM and insufficient glycemic control. The primary endpoint in this study is the change in HbA_{1c} from baseline after 24 weeks of treatment. HbA_{1c} will be measured in the unit of % at all clinical visits. It is planned to show superiority of linagliptin to placebo.

The primary analysis is a restricted maximum likelihood (REML) -based mixed model repeated measures (MMRM) approach. The statistical model will include fixed classification effects for treatment, type of insulin, week, the linear covariate baseline HbA_{1c}, treatment by week interaction, and baseline HbA_{1c} by week interaction.

With regard to efficacy and safety endpoints, the term "baseline" refers to the last observed measurement prior to administration of any randomised study medication.

7.2 NULL AND ALTERNATIVE HYPOTHESES

The superiority of treatment with linagliptin to placebo will be tested for HbA_{1c} change from baseline to week 24 at the level of $\alpha=0.05$ (two-sided).

The primary hypothesis can be written as follows:

H₀: Mean change from baseline in HbA_{1c} after 24 weeks of treatment with linagliptin = Mean change from baseline in HbA_{1c} after 24 weeks of treatment with placebo

H₁: Mean change from baseline in HbA_{1c} after 24 weeks of treatment with linagliptin \neq Mean change from baseline in HbA_{1c} after 24 weeks of treatment with placebo

7.3 PLANNED ANALYSES

The statistical analysis will be based on the following populations.

Treated Set

The treated set (TS) will consist of all patients who were randomised and treated with at least one dose of study drug.

Full Analysis Set

The full analysis set (FAS) will consist of all patients in the TS who had a baseline and at least one on-treatment HbA_{1c} measurement.

